Official title: Efficacy of kinect-based versus tablet-based cognitive training through simulations of instrumental activities of daily living: a pilot study with psychiatric patients

Unique protocol ID: I/2021

Document date: 20 October 2021

DELIBERATION CE/CSCP No. 1/2021, of JANUARY 19th

Deliberation on the request for ethical approval of the research project entitled "Efficacy of kinect-based versus tablet based cognitive training through simulations of instrumental activities of daily living: a pilot study with chronic psychiatric patients" submitted to the Ethics Committee of Casa de Saúde Câmara Pestana (CSCP).

A – REPORT

A.1 The CSCP's Ethics Committee and the Clinical Board, responsible for coordinating clinical investigation processes in CSCP, analyzed the request for ethical approval of a study submitted by [name]. She is currently performing a professional internship in psychology and proposed a research project entitled "Efficacy of kinect-based versus tablet-based cognitive training through simulations of instrumental activities of daily living: a pilot study with chronic psychiatric patients." For this purpose, the models 187, 189, and 218 were carefully analyzed. The study's main goal is to contribute to the stimulation and maintenance of cognitive functioning through a combined intervention (cognitive training + physical activity/kinect-based intervention) or an individual intervention (cognitive training/tablet-based intervention).

A.2 To formalize our decision, we analyzed the following documents that were submitted by the researcher, [name]: a) study protocol, b) response to the request to conduct the study, c) statement of commitment, d) research project, and e) informed consent.

A.3 This study consists of a randomized controlled longitudinal trial that aims to: a) identify which type of intervention is more suited to patients with chronic psychiatric disorders, i.e., the combined intervention or the individual intervention; and b) to evaluate the impact of both interventions in the long-term (3 months follow-up) in several domains (e.g., cognitive functioning, quality of life, mood, and functional capacity).

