Cognitive deficits are a nuclear feature of several psychiatric disorders, leading to decreased functional abilities and quality of life. Besides facilitating the inclusion of more ecologically valid stimuli and training tasks, technology-based cognitive training methods allow more dynamic interactions with the cognitive training content, which can enhance patients' motivation and engagement in the therapeutic process. The modality of interaction with the cognitive training content may influence patients' response to cognitive training interventions. For instance, cognitive training through the tablet essentially requires hand movements (e.g., interaction with the training tasks by touching the correct stimuli). In contrast, cognitive training through the Kinect – a more natural user interface – involves performing broad range movements (e.g., interaction with the training tasks by making specific "body" movements to select the correct stimuli). Literature shows that natural user interfaces provide a training experience closer to reality. As a result, we hypothesize that cognitive training using natural user interfaces can lead to more significant gains in cognitive and non-cognitive domains and, possibly, enhance transfer for daily life outcomes.

Objectives

This study aims to analyze which cognitive training experimental condition – Tablet versus Kinect – results in greater cognitive, mood, quality of life, and functional gains in a sample of chronic psychiatric patients.

Methods

Trial Design

Single-blind pilot randomized controlled trial.

Inclusion criteria

- Chronic Psychiatric diagnosis;
- Maximum age: 75 years old;
- Being able to read and write;
- Relatively preserved language abilities (expressive and receptive language);
- Preserved visual and auditory acuity;
- Having no motor limitations;
- Having no medical history of neurological conditions (e.g., stroke, traumatic brain injury, multiple sclerosis, etc.)

Exclusion criteria

- Experiencing an acute psychiatric episode.

Procedure

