Eligible patients will be randomly allocated to both training conditions – kinect and tablet-based cognitive training. Then, a certified psychologist will collect patients' sociodemographic and clinical data and perform a baseline neuropsychological assessment. The 14-session cognitive training program inspired by instrumental activities of daily living will be applied to all patients. Sessions will be around 30 minutes and will be administered 2 times per week. The computerized cognitive training application used will be Musiquence, which was initially developed for cognitive stimulation purposes within the context of dementia syndromes. Both groups will perform the

same cognitive training program; the only thing that will differ will be the setup (kinect versus tablet).

Neuropsychological assessment

A comprehensive neuropsychological assessment will be delivered to all patients in three different moments, namely:

- Pre-intervention: baseline assessment, immediately before the beginning of the intervention;
- Post-intervention: immediately after the intervention;
- Follow-up: 3-months after the intervention.

The neuropsychological assessment protocol encompasses a set of primary and secondary outcome measures that will be briefly described below:

Primary outcome measures

- Global cognitive functioning: Montreal Cognitive Assessment (MoCA) (Freitas et al., 2013);
- Processing speed: Symbol Search and Digital Symbol Coding from Wechsler Adult Intelligence Scale – Third Edition (WAIS-III; Wechsler, 1997; 2008);
- Attention: Toulouse-Piéron Cancellation Test (TP) (Toulouse & Piéron, 1986);
- Verbal memory: Free and Cued Selective Reminding Test (FCSRT) (Lemos et al., 2015);
- Visual memory and visuospatial abilities: Rey Complex Figure Test (RCFT) (Rey, 1998);
- Executive functions: Frontal Assessment Battery (FAB) (Lima et al., 2008), Semantic and Phonemic Verbal Fluency Tests (Cavaco et al., 2013);

Secondary outcome measures

- Depressive symptoms: Beck Depression Inventory II (BDI-II) (Beck et al., 1996);
- Quality of life: World Health Organization Quality of Life – Bref (WHOQOL-Bref) (Quality of life) (Canavarro et al., 2006);
- Functional abilities: Adults and Older Adults Functional Assessment Inventory (IAFAI) (Sousa et al., 2013).

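### Does the ethics report's aim of combined versus individual intervention conflict with a Procedure that gives both arms one programme on two setups?

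*Protocol*

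**What the plan says.** The document describes the contrast between arms in four places.

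- **Ethics deliberation, A.1.** The committee summarises the main goal as stimulating and maintaining cognition through "a combined intervention (cognitive training + physical activity/kinect-based intervention) or an individual intervention (cognitive training/tablet-based intervention".
- **Ethics deliberation, A.3.** Its first aim is to "identify which type of intervention is more suited to patients with chronic psychiatric disorders, i.e., the combined intervention or the individual intervention".
- **Protocol background and Objectives.** The background says that "cognitive training through the tablet essentially requires hand movements", whereas training through the Kinect "involves performing broad range movements", given there as the means of selecting the correct stimuli. The objective is to find "which cognitive training experimental condition – Tablet versus Kinect – results in greater cognitive, mood, quality of life, and functional gains".
- **Methods, Procedure.** All patients receive a 14-session programme. "Sessions will be around 30 minutes and will be administered 2 times per week". Both groups perform the "same cognitive training program; the only thing that will differ will be the setup (kinect versus tablet".

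The term physical activity appears in A.1 but not in the background, Objectives or Methods. The Neuropsychological assessment section lists tests and scales of cognition, depressive symptoms, quality of life and functional abilities.

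**The concern.** Someone who reads A.1 and A.3 first expects a two-component Kinect arm: cognitive training and, in addition, physical activity. On reaching the Procedure, that reader finds one programme, no exercise content, no amount or intensity, and no measure of activity among the outcomes.

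If a separate exercise component existed, this would matter in three ways.

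- Exercise inside a session of about 30 minutes would displace cognitive training in one arm only. Exercise outside the session would give the arms different schedules.
- A finding of no difference on the aim in A.3 could not be told apart from a Kinect arm in which little activity took place.
- Staff delivering the sessions, or anyone repeating the pilot, would not know which version had been tested.

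The two descriptions also suggest different rationales. A.1 points to the benefit of adding physical activity. The background points to a training experience that is closer to reality.

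**Working it through.** The plan states no figure on this point that could be reproduced, so the check is mainly a comparison of the text.

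**Step 1: which arms do the labels in A.3 refer to?** A.3 uses only the words combined and individual. A.1 defines both by a slash: physical activity is paired with the Kinect, and cognitive training alone with the tablet. Substituting these into A.3 turns its aim into Kinect versus tablet.

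**Step 2: does the protocol's own objective agree?** Yes. The Objectives section names tablet and Kinect as the two experimental conditions.

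**Step 3: where does physical activity come from?** The background gives a source. Kinect users select stimuli with broad body movements, and tablet users select them with the hand. The movement is part of using the device and needs no separate exercise block.

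**Step 4: does the Procedure leave room for additional exercise?** Take the two possibilities in turn.

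| Reading of physical activity in the Kinect arm | Same programme in both arms? | Setup the only difference? |
|---|---|---|
| Body movement needed to operate the Kinect | Yes | Yes |
| Extra exercise inside the session | No, if it displaces training; yes, if the session is lengthened | No |
| Extra exercise outside the session | Yes | No |

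Only the first row satisfies the Procedure. The other two conflict with its explicit statement, so the text does not leave them open.

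**Step 5: the size under each reading.** The inputs are 14 sessions, about 30 minutes each, 2 per week (Procedure).

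- Duration: 14 / 2 = 7 weeks.
- Training time per patient: 14 × 30 = 420 minutes, about 7 hours, in either arm.
- Displacement if the movement is the operation of the interface: 0 minutes.
- Displacement if 5 to 15 minutes of each session went to extra exercise: 14 × 5 = 70 minutes (70 / 420 = 16.7%) to 14 × 15 = 210 minutes (210 / 420 = 50%).

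The 5 to 15 minutes is an assumption with no basis in the document, and it belongs to the second row, which the Procedure excludes. The applicable figure is 0.

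**Step 6: the outcome list.** There are 9 primary tests (MoCA, Symbol Search, the WAIS-III symbol coding subtest, Toulouse-Piéron, FCSRT, RCFT, FAB, semantic fluency, phonemic fluency) and 3 secondary scales (BDI-II, WHOQOL-Bref, IAFAI), so 9 + 3 = 12. None records movement during sessions. That is expected: these are assessments at baseline, after the intervention and at 3 months, not records of what was delivered in a session.

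**The case for a change.** The best argument on the other side is that no sentence says outright that the physical activity in A.1 is the body movement in the background. The committee reviewed the project under a label that suggests an added component. A reader of A.3 might then take a Kinect advantage as support for adding exercise to cognitive training, while a reader of the background would credit the realism of the interface. The design can support only a package effect, and the document does not say so. Session length is also only approximate, and a per-session log of active minutes and tasks completed would help anyone planning a larger trial.

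Part of this stands. The protocol body never uses the term physical activity and sets no amount of movement. A clause linking the two terms would make the document easier to read. The trial cannot separate body movement from interface realism, and a Kinect advantage should be reported as the effect of the whole setup.

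The rest does not make an error in the plan. A.1 and A.3 are the committee's report on the project, and the protocol's objective and Procedure agree with each other. The missing equation does not leave two versions of the Kinect arm open, because the Procedure admits only one. A session log is a detail of delivery that can sit in case report forms or a session manual. Its absence from a list of neuropsychological outcomes contradicts nothing. Such a log would not separate movement from realism either.

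**Conclusion.** The concern does not hold. A.3, read with the mapping in A.1, compares the same two arms as the Objectives and the Procedure. The Procedure fixes their content as one programme on two setups. Cognitive training displaced by design is 0 of about 420 minutes per patient. If the plan is followed as written, the randomised comparison is Kinect-based training, with the movement it requires, against tablet-based training, and that comparison is sound as a package.

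This rests on two readings: that the Procedure's statement about the sole difference is meant literally, and that the slash in A.1 equates each label with one device. Both are the plain sense of the text, and the background's account of the two interfaces supports them. What is left is a point of terminology with no effect on the arms, the data or the analysis.

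### Does testing immediately after the intervention mix short-lived exertion effects from the Kinect sessions into the post-intervention comparison?

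*Protocol*

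**What the plan says.** Under Neuropsychological assessment, the protocol lists three occasions for the same battery. The first is "Pre-intervention: baseline assessment, immediately before the beginning of the intervention", the second is "Post-intervention: immediately after the intervention", and the third comes 3 months after the intervention. The Procedure describes what is delivered between the first two: "The 14-session cognitive training program inspired by instrumental activities of daily living will be applied to all patients". It adds: "Sessions will be around 30 minutes and will be administered 2 times per week".

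The arms differ in how patients interact with the tasks. The background says that "cognitive training through the tablet essentially requires hand movements", whereas Kinect training "involves performing broad range movements". In the ethics deliberation (A.1) the Kinect condition is a "combined intervention (cognitive training + physical activity/kinect-based intervention", so physical activity is a declared part of that arm.

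The protocol states no interval in hours or days between session 14 and the second assessment. It does not say that the two fall on the same day.

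**The concern.** Baseline precedes every session in both arms. If the second battery came straight after session 14, it would follow about half an hour of whole-body interaction in one arm and hand movement in the other. Any brief after-effect would then be present at that occasion only and would differ by arm.

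Randomisation would not protect against this, because the assigned condition causes the difference. Gain scores and baseline adjustment would not remove it either, because no session precedes baseline. Several primary measures test processing speed, attention and verbal fluency, where a patient's momentary state could plausibly matter. A transient rise or fall at the second assessment could also make the change to 3 months look like lost or late gains. The stake would be the Kinect-tablet contrast at one of the two occasions after baseline.

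**Working it through.** The protocol gives no figure to reproduce on this point: no sample size, standard deviation or effect size, and nothing on acute effects. The check is therefore mainly a reading of the text, followed by a look at what the illustrative numbers can and cannot show.

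**1. What the intervention is.** The Procedure defines a programme of 14 sessions at two per week: 14 / 2 = 7 weeks. The assessment list refers to the intervention in all three entries: before its beginning, after it, and 3 months after it. The word has to mean the same thing in each. The first entry speaks of the beginning of the intervention and the third counts 3 months from its end, so the word denotes the 7-week programme and not a single session. On that scale, immediately after means at the end of the programme rather than at follow-up.

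**2. Whether back-to-back testing is implied.** The battery comprises the MoCA, two WAIS-III subtests, the Toulouse-Piéron test, the FCSRT, the Rey figure, the FAB and two fluency tests: 1 + 2 + 1 + 1 + 1 + 1 + 2 = 9 cognitive measures. Adding the BDI-II, WHOQOL-Bref and IAFAI gives 9 + 3 = 12. The protocol states no duration, so this is inference, but giving 12 measures directly after a session of about 30 minutes is not the obvious plan. A short-lived state would also be unlikely to act evenly across so long a battery.

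**3. Whether the mechanism is documented.** The protocol does not mention exertion, fatigue or arousal. The background explains the Kinect movements as the means by which patients choose the correct stimuli, in other words selection gestures. A.1 calls this physical activity but gives no intensity. Physical activity is also part of the planned contrast, so only a carry-over from the last session would be unwanted.

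**4. What the illustrative numbers show.** Let *a* be an assumed acute difference between arms, in SD units, at the second assessment, with no true training difference. Let rho be the pre-post correlation and n the number per arm. With equal variances, the standardised difference in gains is d = a / sqrt(2(1 − rho)). The two-sided 0.05 t-test has 2n − 2 degrees of freedom and noncentrality d × sqrt(n/2). For example, a = 0.2 and rho = 0.7 give d = 0.2 / sqrt(0.6) = 0.258; with n = 30 the noncentrality is 0.258 × sqrt(15) = 1.00 and the rejection probability is 0.166.

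| a (SD) | rho | n = 10 | n = 20 | n = 30 |
|---|---|---|---|---|
| 0 | any | 0.050 | 0.050 | 0.050 |
| 0.2 | 0.5 | 0.071 | 0.095 | 0.119 |
| 0.2 | 0.7 | 0.085 | 0.125 | 0.166 |
| 0.3 | 0.5 | 0.097 | 0.152 | 0.208 |
| 0.3 | 0.7 | 0.130 | 0.223 | 0.314 |

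The arithmetic is right, but a, rho and n are all assumptions. The table shows that a bias, once assumed, raises the rejection rate. It is no evidence that this trial has one, and at a = 0 the rate is the nominal 5%.

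**5. What the follow-up adds.** No training session precedes the 3-month assessment, and A.3 makes long-term impact an explicit aim. An arm difference still present at 3 months cannot be a carry-over from session 14.

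**The case for a change.** The strongest counter-argument is that timing of assessments belongs in the protocol, so the gap cannot be left to an analysis plan. The text sets no minimum interval, so it permits same-day testing and different intervals for different patients. If an acute difference did arise, no analysis of the second assessment alone could separate it from a training gain; only scheduling could. A stated window, the same in both arms and away from a training day, would cost a few days' delay and no extra test.

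Most of this is true as far as it goes. The interval is unstated, the arms do differ in movement, and a transient effect would enter the contrast undiminished if it occurred. But to permit same-day testing is not to prescribe it, and the step from larger movements to shifted scores rests on nothing in the protocol. That a change is cheap does not show that the present text is wrong. Choosing a day without training would be a reasonable scheduling preference, with no demonstrated gain.

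**Conclusion.** The concern does not stand. The wording is a phase label for the end of a 7-week programme, and nothing in the protocol ties the battery to the day of session 14. The feared bias needs two things the protocol does not supply: testing directly after the last session, and an acute effect of Kinect movement on test scores. The size and direction of that effect are unknown and it may be zero. The 7% to 31% rejection rates are conditional on an assumed bias of 0.2 or 0.3 SD, a correlation of 0.5 to 0.7 and 10 to 30 patients per arm, so they carry no weight here.

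The conclusion rests on reading the intervention as the whole programme, as the Procedure and the other two entries in the assessment list support. An instruction elsewhere to test straight after session 14 would reopen the question, and then only for the post-intervention comparison. As written, the protocol leaves a visit window unspecified; it contains no error or contradiction on this point.
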